Background	
Having a child admitted to the Pediatric Intensive Care Unit (PICU) is a challenging and stressful experience for parents and caregivers. Despite the high survival when compared to adult ICUs¹, a PICU admission can have meaningful long term negative health consequences for adult caregivers including symptoms of depression, anxiety and PTSD².
 
There is little known in regards to what specific factors impact the mental health of caregivers of PICU patients. However, research into stress and anxiety has suggested that uncertainty is a significant contributor to stress when faced with a new environment.³ This uncertainty is palpable in the PICU for many reasons.
 
First, few caregivers are medically savvy enough to appreciate the diversity and scope of pathology that is routinely treated in the PICU. They may not know that PICU is an acronym for Pediatric Intensive Care Unit or that the sickest children in the hospital are cared for in that unit.⁴ They may have no experience with pediatric illness beyond a simple viral process. Therein lies a major source of stress and uncertainty and basis of a question intensivists often field, "Have you ever seen a child this sick?"
 
Intensivists can and often do attempt to mitigate this uncertainty with illness specific anticipatory guidance. However, providing that guidance, and often re-assurance, in the PICU can be challenging due to the uncertain trajectory of pediatric illness. It is frequently difficult to counsel caregivers on what to expect during their hospitalization without becoming too hypothetical or presenting conflicting possible scenarios.⁵
 
Prior research suggests that invasive procedures can be a significant source of immediate stress for caregivers. This uncertainty is compounded by the fact that it is common practice to introduce the idea of invasive procedures, and subsequently obtain consent, only when that procedures is likely to be required. This leads to obtaining informed consent, a concept with legal significance, in the setting of a deteriorating child and subsequently a caregiver under significant duress.

This forces us to consider the question, are we obtaining morally and legally valid informed consent or, despite our best efforts, are we obtaining coerced consent?

To further illustrate the possibility of coerced consent, one can consider how often parents or guardians refuse to give consent for invasive procedures? In general practice, and the experience of the PICU in which I currently practice, caregiver refusal is a very rare occurrence. This may be because in pediatric critical care practice there are few good alternatives to the types of invasive procedures that we commonly perform (intubation, central venous catheterization, arterial catheterization, and procedural sedation). However, it may be because intensivists are, unintentionally, overwhelming caregivers who are in acutely stressful and emotionally vulnerable states.

The complex landscape of the PICU described above presents a unique opportunity to simultaneously obtain consent under less stressful circumstances and set realistic expectations as to the nature of a PICU admission, a means of alleviating some of the uncertainty of a PICU stay by introducing the types of procedural support we can offer and obtaining informed consent prior to their immediate necessity. In this study we will use a prospective cluster randomized design to compare caregiver stress level via the Short Stress Overload Scale (SOS-S) in a control arm our current model of obtaining ad-hoc for invasive procedures. In the experimental arm, employing a scripted bundle consent upon admission to the PICU, which will serve the dual purpose of consenting parents and/or legal guardians for 5 commonly performed invasive procedures as well as general expectation setting for the PICU)

Hypothesis

Caregivers that are consented for invasive procedures via a bundle consent at the time of admission to the PICU will report less stress at 48-72 hours post admission and at the time of discharge than those consented via the current ad-hoc model of consent.

Study objectives

1. To quantify caregiver stress and determine if a bundle consent and expectation setting can decrease that stress.
2. To determine the change in the proportion of procedures performed without appropriate and documented written consent, between the current ad-hoc model of consent and a bundle consent process.

Study population

Parents or caregivers of patients admitted to a PICU during the designated study period

Main inclusion criteria	Parents or caregivers of critically ill children admitted to the Pediatric ICU during the designated study period.
Main exclusion criteria	Anticipated length of PICU stay < 24 hours, Non-English speaking patients
Study intervention	Scripted consent for the following invasive procedures (central venous catheter, arterial catheter, intubation, procedural sedation) by a PICU Attending, Fellow, or Nurse Practitioner within 12 hours of admission to the Pediatric ICU.
Data collection	Patient and caregiver demographic, as well as patient diagnostic, therapeutic and procedural data will be collected as well as caregiver self-reported stress scores via the Short Stress Overload Scale (SOS-S)
Clinical endpoints	Discharge from the Pediatric ICU or if interim analysis dictates that harm is being done as discussed under Ethical Considerations heading.
Confounding variables	
 • Patient demographic data (age) • Patient PELOD-2 Score • Type of admission (planned, direct from ED, transfer from floor, transfer from outside Hospital) • Prior NICU or PICU stay admission • Caregiver demographic data (Age, Sex, Ethnic background, highest education level) • Caregiver assessment of “Life-threatening” nature of illness using a Likert scale
Ethical considerations	
As this study evaluates consent, and particularly the possibility of coerced consent, it is not possible to create a design that involved consent for participation that does not jeopardize the integrity of the study. Furthermore, our experimental intervention, a bundled consent process, is currently being utilized at various pediatric and adult ICUs in the United States and will meet all of the legal requirements for informed consent in the state of Virginia. We will therefore ask for a waiver of individual informed consent for randomization. We will be asking for caretaker consent for the collection of demographic data and measurement of caretaker stress.
 
The scripted bundle consent process will add no risk of physical harm to the Pediatric ICU patient. We recognize the possibility that our intervention may result in an increase in stress and/or anxiety to parents and/or caregivers in the experimental group and therefore plan to conduct interim analyses (after the first 50 and 100 patients) to ensure that no harm is being done, with the intent of terminating our study if we show an increase in caregiver stress of 20% or more in the experimental group.
 
Furthermore, for the study participants in both groups, we plan to use caregiver stress scores as a basis for referral to already existing internal mechanism for caregiver stress mitigation,

	
including but not limited to: Social Work, Case Management and Child Life services if a caregiver's score fall in the "High Stress" quadrant (High Personal Vulnerability and High Event Load Scale)

Methodology	
Control and Experimental groups will be created using a cluster randomization design in alternating periods beginning of the 1st and 15th of each month.
 
Caregivers included in the control group will be admitted to the PICU and undergo consent for invasive procedures as is indicated by the clinical needs of their children as per current unit practices.
 
Caregivers included in the experimental group will, within 12 hours of admission, be consented for: central venous catheter, arterial catheter, intubation, and procedural sedation via a scripted bundled consent by an PICU Attending, Fellow, or Nurse Practitioner.
 
Then, for both groups, at 48-72 hours after admission and at the time of discharge from the PICU, they will receive and complete the SOS-S, either electronically or on paper, to measure stress, which will then be collected and recorded.
 
Any caregiver in the experimental or control group identified to fall into the "High Stress" group as per the SOS-S will be referred to pre-existed support services within the PICU/VCUHS infrastructure.
 
All data recorded will be completely de-identified and collected within REDCap.

Statistical plan	
First, we will identify the confounding factors using a bivariate regression model between each of the following factors and the primary outcome: patient age, type of admission, prior ICU admissions, caregiver demographic data, and caregiver assessment of life-threatening illness.
 
Second, the association between the bundle consent process and the outcome (caregiver stress) will be investigated using logistic regression models, adjusting for the confounding factors identified in step one.
 
Third, a multivariable logistic regression will be performed with all variables (full model). The simplification of this full model will be done using another multivariable logistic regression with backward selection at the level $p = 0.05$.

Sample size	
After examining prior studies which used the SOS-S to quantify pathologic stress reactions, We estimate a mean SOS-S score of 19.9 and a standard deviation of 11.3. We anticipate a 20% reduction in SOS-S score in the experimental group (i.e. from

	19.9 to 15.9). Setting an alpha of 0.05 and power of 0.8. We anticipate requiring a sample size of 266 caregivers to sufficiently test the null hypothesis.
Location	Pediatric Intensive Care Unit at the Children's Hospital of Richmond, VCUHS

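### Must the harm-stopping rule name its SOS-S time point, the base of the 20% and a statistical test before it can be used?

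*Combined protocol and SAP*

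**What the plan says.** The Ethical considerations row acknowledges that the bundled consent might raise caregiver stress. The investigators therefore "plan to conduct interim analyses (after the first 50 and 100 patients"), "with the intent of terminating our study if we show an increase in caregiver stress of 20% or more in the experimental group". The Clinical endpoints row adds nothing of its own: the study ends at PICU discharge or "if interim analysis dictates that harm is being done as discussed under Ethical Considerations heading". The same Ethical considerations row explains the setting: "We will therefore ask for a waiver of individual informed consent for randomization".

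Three other rows bear on how the rule is read:

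- Methodology collects the SOS-S twice, "at 48-72 hours after admission and at the time of discharge from the PICU", and allocates the arms "in alternating periods beginning of the 1st and 15th of each month".
- Sample size works on the mean score: "We estimate a mean SOS-S score of 19.9 and a standard deviation of 11.3", with an anticipated 20% fall to 15.9.
- Statistical plan says "the association between the bundle consent process and the outcome (caregiver stress) will be investigated using logistic regression models", which would need a binary outcome.

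No level, confidence bound or error rate is given for the harm rule.

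**The concern.** Randomisation is to proceed under a waiver of consent, so an ethics board would want to know how the harm rule behaves. As written, one analyst could use the 48-72 hour score and another the discharge score. One could take 20% as 3.98 points on the assumed mean of 19.9, another as a ratio to the observed control mean, and a third as a rise in the share of stressed caregivers. One could act on the point estimate and another ask for significance. The same data could then lead to different decisions.

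The looks are also small. A difference of 3.98 points is little more than one standard error at 50 caregivers, so a plain threshold will sometimes be crossed by chance. After the 100th caregiver there is no further harm look for the remaining 166 of 266 (62%). It is natural to ask whether a stated one-sided test at the same looks would do better.

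**Working it through.** **Inputs.** Mean 19.9, SD 11.3, 20% change and N = 266 (Sample size); looks at 50 and 100 (Ethical considerations); 83 admissions a month and 80% participation (Study duration); half-month periods (Methodology). Assumed: one scored caregiver per patient, independent scores, one time point.

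**The plan's own figure.** No error rate is stated for the harm rule, so the only figure to reproduce is 266. The two-sided normal formula with alpha 0.05 and power 0.80 gives, per arm, 2 × (1.960 + 0.842)² × 11.3² / 3.98² = 126.5, hence 254 in total (252 with 4.0 points). The usual rank-test inflation gives 126.5 × π/3 = 132.5, rounded up to 133 per arm, or 266. The inputs are therefore coherent with a comparison of scores and a 20% relative change.

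**Arm sizes at the looks.** Accrual is 83 × 12/365 × 0.8 = 2.18 a day. Starting on the 1st (14-day, then 16-day periods), the arms stand at 31/19 and then 61/39. Starting on the 15th (16, then 14 days), they stand at 35/15 and then 69/31.

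**Formulas.** SE = 11.3 × √(1/a + 1/b). For cumulative data the correlation between looks is ρ = SE₂/SE₁, about 0.70. The chance of stopping is 1 − Φ₂(c₁, c₂; ρ), where each c is the threshold minus the true difference, in SE units.

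With balanced arms, SE₁ = 11.3 × √(2/25) = 3.20 and SE₂ = 11.3 × √(2/50) = 2.26. The threshold is 3.98/3.20 = 1.25 and 3.98/2.26 = 1.76 SE. The tail areas are 10.7% and 3.9%, and 12.0% of no-harm trials stop at one look or the other.

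| Arms at looks 1 and 2 | Threshold in SE | False stops, fixed 3.98 | False stops, ratio to control | False stops, one-sided 0.08 |
|---|---|---|---|---|
| 25/25, 50/50 | 1.25, 1.76 | 12.0% | 14.9% | 12.4% |
| 31/19, 61/39 | 1.21, 1.72 | 12.9% | 15-16% | 12.4% |
| 35/15, 69/31 | 1.14, 1.63 | 14.5% | 16-19% | 12.5% |

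A 17-day opening period, which occurs when starting on the 15th of a 31-day month, gives 37/13 at look 1. False stops are then just under 16% (fixed) or 17-20% (ratio).

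**Detection of a true 20% increase.** The true difference then equals the threshold, so each look is an even chance whatever the SD. The two-look total is 1 − [1/4 + arcsin(ρ)/2π], or 62.5% at ρ = 0.707 and about 63% for the other splits. The 0.08 test gives:

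| Arms | Look 1: threshold, test | Overall: threshold, test |
|---|---|---|
| 25/25, 50/50 | 50%, 44% | 63%, 69% |
| 31/19, 61/39 | 50%, 42% | 63%, 67% |
| 35/15, 69/31 | 50%, 40% | 63%, 64% |

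The test asks for 1.405 × SE. At planned accrual that is an observed rise of about 23-25% at look 1 and 16-17% at look 2. It relaxes the second look by tightening the first.

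**Sensitivity to the SD.** Starting on the 15th with SD 12, the test detects 60.6% against 62.6% for the threshold. With SD 13 the figures are 56% and 63%.

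**Period effects.** At an assumed period ICC of 0.01, false stops are 16% for the test and 16-21% for the threshold. At 0.05 they are 25% and 24-29%.

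**Cost to the trial.** A harm stop cannot lead to a claim of benefit, so it does not inflate the 0.05 level of the main comparison. Under the hypothesised 20% reduction, the threshold wrongly stops 0.8-2.4% of trials at planned accrual, which bounds the loss of power.

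**The case for a change.** The strongest case for a change is that the text leaves a wide range of behaviour open. If significance at one-sided 0.025 were required, false stops would fall to about 4% but detection to about 41-44%. On the plain-threshold reading the figures are roughly 12-20% and 63%. If either SOS-S score could trigger (assumed correlation 0.3-0.8), false stops would be 18-31%. If 20% meant a relative rise in the proportion stressed (assumed 20-50%), they would be 31-50%. A few sentences would settle this without touching the looks, the sample size or the data collection.

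Part of this stands. Neither the time point nor the criterion is written down, and nothing redacted accounts for that. The wide range, however, comes mostly from readings the documents do not favour. The study compares SOS-S scores, and its one worked example of a 20% change is in the mean score. The high-stress category is used only to refer caregivers to support services. The proportions and correlations behind the most extreme figures are assumptions. As for the criterion, with a given SD a fixed 3.98-point threshold is already a one-sided boundary, at 1.14-1.25 SE and then 1.63-1.76 SE. The choice is therefore about where to place the boundary, not between a test and no test.

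The missing look after 100 caregivers is a fair observation, but a stated test at the same two looks would not address it.

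**Conclusion.** No change to the plan follows. The unstated details are ones that whoever runs the interim analysis would settle before looking at the data. The mean SOS-S and a relative 20% come from the Sample size row. The 48-72 hour score is the natural choice for an early check because it is fixed in time and usually available sooner, though that last step is inference and not text.

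On this reading the rule behaves as a sensitive harm trigger: about 12% false stops with balanced arms, about 13-20% with the splits implied by the calendar, and about 63% detection of a true 20% increase. Sensitivity is defensible where allocation proceeds under a waiver. The one concrete alternative, a one-sided 0.08 test, has no false-stop advantage with balanced arms (12.4% against 12.0%). It gives up 8-10 points of detection at the 50-patient look at planned accrual, loses its overall advantage at an SD of 12 with a start on the 15th, and helps little if periods differ. Other levels move along the same trade-off: 0.05 gives about 8% false stops and 54-58% detection, and 0.10 about 15% and 69-72%. Reasonable statisticians would choose differently.

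These figures rest on SD 11.3 unless stated, one scored caregiver per patient, a single time point and no period effect. At 50 patients there is only one period per arm at planned accrual, so no version of the rule can separate period from arm at that look.

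### PELOD-2 is listed as a confounder but left out of the screen that feeds the bundle-effect model, and neither the adjustment set nor the primary model is fixed in advance

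*Combined protocol and SAP*

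**What the plan says.** The Confounding variables section of the combined protocol and SAP lists six groups: patient age, "Patient PELOD-2 Score", type of admission, prior NICU or PICU stay, "Caregiver demographic data (Age, Sex, Ethnic background, highest education level"), and the caregiver's view of the life-threatening "nature of illness using a Likert scale".

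The Statistical plan then has three steps:

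1. Step one will "identify the confounding factors using a bivariate regression model between each of the following factors and the primary outcome". The factors are "patient age, type of admission, prior ICU admissions, caregiver demographic data, and caregiver assessment of life-threatening illness". No threshold or other retention rule is given.
2. In step two, "the association between the bundle consent process and the outcome (caregiver stress) will be investigated using logistic regression models", adjusted for whatever step one identified.
3. Step three fits a multivariable logistic model with every variable, without listing them, and reduces it by backward selection at p = 0.05.

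Three other sections bear on this. The bundle is given "within 12 hours of admission to the Pediatric ICU" (Study intervention). Participation in the measurements is voluntary: "We will be asking for caretaker consent for the collection of demographic data and measurement of caretaker stress" (Ethical considerations). Arms alternate from the 1st and 15th of each month (Methodology), with 80% participation expected over four months (Study duration). The documents do not say when PELOD-2 is scored or when the life-threat rating is taken.

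**The concern.** PELOD-2 is the only clinical severity score on the sponsor's own list, and the only listed item that step one leaves out. No reason is given. Because step two inherits its covariates from step one, the omission carries straight into the model meant to answer the main question. Type of admission and the caregiver's own rating are at most partial substitutes.

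The wider difficulty is that the adjustment is not fixed. Covariates are chosen by their association with the outcome in the same data, under no stated rule. The plan then produces a step-two model, a full model and a reduced model, and none is designated for the reported estimate and test.

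At stake are whether severity differences between the two sets of periods can be corrected, and whether the reported bundle effect was determined before the data were seen. The life-threat rating adds a smaller problem: if it is taken after the bundle discussion, the bundle may have changed it.

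**Working it through.** **Side-by-side reading**

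| Listed confounder | Screened in step one | Available to step two |
|---|---|---|
| Patient age | yes | if identified |
| PELOD-2 | no | no |
| Type of admission | yes | if identified |
| Prior NICU/PICU stay | yes (prior ICU admissions) | if identified |
| Caregiver demographics | yes | if identified |
| Life-threat rating | yes | if identified |

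The p = 0.05 level belongs to backward selection in step three, so it does not supply a rule for step one.

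**Inputs.** From the Sample size section: SD 11.3, means 19.9 and 15.9 (difference 4.0), N = 266, so 133 per arm. The usual two-sided formula gives 2 × (1.960 + 0.842)² × 11.3² / 4² = 125.3, so 126 per arm and 252 in total. The plan's 266 is not reproduced without an unstated allowance (252 / 0.95 = 265.3, so 266). That is a separate matter, and 266 is taken as given. Two periods a month for four months make about 8 periods of 266 / 8 = 33.25 caregivers. The R² of PELOD-2 with SOS-S, the period ICC and the SOS-S cut-point are not in the documents. The values below are assumptions.

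**1. Power under the planned logistic model** (simulated; SOS-S cut at the control 50th / 70th percentile; clustering ignored). Unadjusted power is about 63 to 66% / 54 to 56%. Adding PELOD-2 at R² 2 to 10% changes it by about 0 to 3 points. Even with balanced arms, the adjusted log-odds ratio is larger than the unadjusted one by up to about 7%, so differently adjusted models do not estimate quite the same quantity.

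**2. Chance imbalance, on the score scale.** The SD of the standardised difference in PELOD-2 is √[(2/133) × (1 + 32.25 × ICC)], which is 0.123 at ICC 0 and 0.198 at ICC 0.05. The 95% limit of the resulting shift is 1.96 × √R² × 11.3 × SD:

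| R² | ICC 0 | ICC 0.05 |
|---|---|---|
| 5% | 0.61 | 0.98 |
| 10% | 0.86 | 1.39 |

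These are SOS-S points, against a target of 4.

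**3. Unequal participation.** Suppose that in one arm only, the 20% who decline have PELOD-2 m SD above that arm's mean. Participants there then sit (0.2/0.8) × m lower: 0.125 SD for m = 0.5 and 0.25 SD for m = 1.0. Multiplying by √R² × 11.3 gives 0.32 / 0.63 points (R² 5%) or 0.45 / 0.89 points (R² 10%).

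**4. Would adding PELOD-2 to step one be enough?** Chance that a univariable logistic screen drops it (n = 266, same two cuts):

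| R² | rule p < 0.05 | rule p < 0.20 |
|---|---|---|
| 2% | 58% / 62% | 30% / 35% |
| 5% | 19% / 25% | 6% / 8% |
| 10% | 2% / 4% | under 1% |

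**5. Choice among models.** A null simulation used 9 assumed covariates, independent caregivers, arm always kept and 4,000 runs at each of two outcome prevalences. Any single model rejected in about 5.2 to 6.0% of trials. Taking the most favourable of the step-two, full and reduced models rejected in about 7.4 to 7.6%.

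**6. Room for covariates if the outcome is binary.** Arm 1, PELOD-2 1, patient age 1, type of admission 3, prior stay 1, caregiver age 1, sex 1, ethnic background 3 and education 3 (four levels each assumed for the last two) make 15 coefficients. Events: 266 × (50% + 36.2%)/2 = 115, or 266 × (30% + 19.0%)/2 = 65. That is 115/15 = 7.6 or 65/15 = 4.3 events per coefficient.

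**The case against.** The best defence is step three. Its full model takes in every variable, and since PELOD-2 is on the sponsor's list, the natural reading is that it is included there, unscreened and before any deletion. On that reading the omission may be a slip in one list. Step two is also the only step framed around the bundle, so what is missing could be called a label. These arguments limit the point but do not remove it: the full model's contents are not stated, it does not repair step two, and it is not designated for reporting.

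A reader might infer four stronger things that the documents do not support.

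- *PELOD-2 is absent from the whole analysis.* The omission is certain only for steps one and two.
- *The trial may end with no bundle estimate.* That would require reporting only the reduced model after arm had been deleted; step two gives an estimate that backward selection does not touch. Nor does the selection cost power. In simulation with a 4-point effect, arm was deleted in 31.5% / 39.1% of trials and was non-significant in the unselected full model in 31.3% / 38.9%.
- *The omission biases the result.* If the arms are comparable, the score-scale difference is not biased on average. Severity-related participation that differs by arm is an assumption; the documents give only voluntary consent and an 80% rate.
- *Adjustment would buy substantial power.* Calculations that treat SOS-S as a continuous score do not describe the logistic analysis planned.

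**Conclusion.** The point stands as an inconsistency between two current sections and as an adjustment strategy that is not fixed in advance. It should be corrected, but its expected numerical effect is modest: about 0 to 3 points of power, chance shifts mostly within 0.6 to 1.4 SOS-S points, and participation shifts of 0.3 to 0.9 points if that mechanism operates, against a 4-point target. Choosing the most favourable model could raise the false-positive rate to about 7.5%. Nothing in the plan says the sponsor intends this; the plan simply does not rule it out.

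The textual part is certain. The sizes depend on the assumed R², ICC, cut-points and covariate effects, and items 1, 4 and 5 ignore period clustering. The stronger reasons to act are protection against severity imbalance with only about 8 periods, and removal of the choice among models.

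**What to change.** - Name the step-two model as the single primary analysis, with arm always in it.
- Replace the outcome screen with a covariate set fixed in advance from the Confounding variables list, including PELOD-2. Adding PELOD-2 to step one alone is not enough, since the screen could still discard it.
- State when PELOD-2 is scored: at or near admission, on the same clock in both arms.
- Include the life-threat rating only if it is taken at the same time from admission in both arms and before the bundle could affect it. A rule tied to the bundle itself has no counterpart in control periods. Otherwise keep the rating out of the primary model.
- Label any backward-selected model exploratory and keep arm in it.

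**Cost.** No new variables are needed, but two measurement times must be written down. If the outcome stays binary, 4 to 8 events per coefficient is thin, so the list must be kept short or sparse levels merged in advance. This change does not settle the SOS-S cut-off, the choice between the 48–72 hour and discharge assessments, or the handling of periods. Those need their own statements before the primary analysis is fully defined.

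### Backward selection at p = 0.05 does not exempt the bundle term, so the reduced model reports a bundle effect only when it is significant

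*Combined protocol and SAP*

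**What the plan says.** The Statistical plan has three steps. Step one screens possible confounders one at a time against the outcome. Step two relates the bundle to caregiver stress by logistic regression, adjusted for the confounders found in step one. In step three, "a multivariable logistic regression will be performed with all variables (full model"), and then: "The simplification of this full model will be done using another multivariable logistic regression with backward selection at the level" p = 0.05.

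Nothing in the protocol says that the bundle term stays in the reduced model whatever its p-value. Nothing says which of the three models (step two, full or reduced) supplies the main estimate. The first entry under Study objectives is to quantify caregiver stress and "determine if a bundle consent and expectation setting can decrease that stress".

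**The concern.** Step two has just named the bundle as the association under study, so a model of all variables naturally includes it. Backward selection at 0.05, followed as written, removes any term above that threshold, the bundle included. This would remain a problem even if the covariate list were perfect.

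If the term is removed, the reduced model has no bundle estimate and no interval, and so cannot bound either a small benefit or a rise in stress. If the term stays, its estimate has been shown because it was significant, and such estimates are on average too far from zero. The reduced model comes last and is presented as the simplification of the analysis, so it could readily be taken as the trial's answer to the first objective.

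**Working it through.** **Inputs, from Sample size and Methodology**

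- Control mean and SD: "We estimate a mean SOS-S score of 19.9 and a standard deviation of 11.3".
- Effect: "We anticipate a 20% reduction in SOS-S score in the experimental group", from 19.9 to 15.9, a difference of 4.0.
- Error rates: "Setting an alpha of 0.05 and power of 0.8". Sidedness is not stated; two-sided is assumed.
- Size: "We anticipate requiring a sample size of 266 caregivers to sufficiently test the null hypothesis".
- Allocation: "Control and Experimental groups will be created using a cluster randomization design in alternating periods beginning of the 1st and 15th of each month". No ratio is given; 1:1 is assumed, so 133 per arm.

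**The plan's own figure.** n per arm = 2 × (1.960 + 0.842)² × 11.3² / 4.0² = 125.3, rounded up to 126, or 252 in total. This does not reproduce 266. An unstated 5% loss would: 252/0.95 = 265.3, rounded up to 266. The gap is in the conservative direction and does not affect this point. Power at 133 per arm is about 82%.

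**Selection on the mean scale.** The plan gives its effect as a difference in means, so this is the only scale on which its own figures can be used directly.

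- SE = 11.3 × √(2/133) = 1.386.
- The term stays if |estimate| > 1.96 × 1.386 = 2.72 points.
- With δ = true effect / SE, P(retained) = Φ(δ − 1.96) + Φ(−δ − 1.96).
- Mean retained estimate = SE × {δ + [φ(1.96 − δ) − φ(1.96 + δ)] / P(retained)}.

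At 4 points: δ = 2.887; P(retained) = Φ(0.927) = 0.823; mean = 1.386 × (2.887 + 0.260/0.823) = 4.44.

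At 2 points: δ = 1.443; P(retained) = Φ(−0.517) + Φ(−3.403) = 0.303; mean = 1.386 × (1.443 + 0.348/0.303) = 3.59.

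| True effect (points) | Dropped | Mean if retained | Ratio to truth |
|---|---|---|---|
| 4 (planned) | 18% | 4.44 | 1.11 |
| 3 (assumed) | 42% | 3.93 | 1.31 |
| 2 (assumed) | 70% | 3.59 | 1.80 |
| 1 (assumed) | 89% | 3.17 | 3.2 |

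**Is every retained estimate too large?** No. At 4 points, retained estimates between 2.72 and 4.0 lie below the truth. Their share is [Φ(0) − Φ(−0.927)] / 0.823 = (0.500 − 0.177) / 0.823 = 39%.

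**Logistic version.** The plan gives no cut-off for the score, so these figures rest on assumptions. The procedure was simulated with n = 266, ten candidate covariates (two with a real effect), 2000 runs per setting, and the bundle term either free or forced in.

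- Planned effect, score split at 19.9: dropped in 32% of runs; mean log odds ratio −0.80 when retained, −0.66 when forced in (ratio 1.22).
- Planned effect, split at 27.5: dropped in 45%; ratio 1.36.
- Half the planned effect, split at 19.9: dropped in 76%; ratio 2.1.
- Chance of a significant bundle term, split at 19.9: about 68% at the planned effect and about 5.6% under no effect, whether free or forced.

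With other assumptions (ten covariates with R² 0.2, 30% or 50% of controls above the cut, 800 runs per setting), the term was dropped in 28–41% of runs at 4 points and about 78% at 2 points.

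Neither the mean-scale calculation nor the simulation with the bundle term free or forced allows for clustering by half-month period.

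**The case against.** The strongest reply is that the bundle question has its own step. In step two the bundle is the named exposure and is not selected on its own p-value, and step three fits an unreduced full model before any elimination. Two unselected estimates therefore exist whatever happens to the reduced model. This stands, and it limits the harm to the case in which the reduced model is reported as the result. It does not remove the point, because the plan does not say which model is primary.

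It is also fair to say that the plan is silent on protection and does not state that the bundle may be deleted. But a selection rule with no exemption, followed as written, deletes it. If step three was meant to cover covariates only, it would not estimate the bundle effect, and the plan should say so.

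A reader might infer three stronger things that the documents do not support:

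- *That the reduced model must give either an exaggerated answer or none.* At the planned effect about 39% of retained estimates are below the truth. The inflation is an average over the trials that keep the term.
- *That the false-positive rate is affected.* The chance of a significant bundle term is essentially the same with the term free or forced in.
- *That monitoring for harm is disabled.* Under Ethical considerations, the interim looks after 50 and 100 patients use a 20% increase in stress as the stopping threshold. Nothing ties that rule to the reduced model.

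**Conclusion.** The point holds as a defect of estimation and reporting in the reduced model. On the plan's SD and sample size, with 1:1 allocation, a two-sided 0.05 threshold and a mean-difference approximation, the bundle term would be missing from about 18% of reduced models at the planned 4-point effect, with a modest average inflation of 11% when present. The problem becomes large only if the true effect is smaller than planned: at an assumed 2 points, about 70% missing and 1.8 times the truth. The logistic figures are larger, but they depend on an assumed cut-off and assumed covariates, so the absence of protection is more certain than the size of the bias. The change should be made, but the trial's ability to answer its first objective does not fail without it.

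**What to change.** Amend step three of the Statistical plan to state that:

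1. the bundle/control term is kept in every model whatever its p-value, and backward selection applies to covariates only;
2. one model fitted without selection on the bundle term, either step two or the unreduced full model, is the primary source of the bundle effect and its 95% confidence interval;
3. the reduced model is descriptive and shows which covariates are associated with stress.

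The second item is needed as well as the first, because otherwise several bundle estimates remain with no stated order among them. The cost is a few sentences. No extra caregivers or data are needed, and the simulation shows no loss in the chance of a significant bundle term.
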